10.3.2 Pharmacokinetic Statistical Methodology

Dose Proportionality (Part A IV doses only)

The log-transformed PK parameters AUC(0-tlast), AUC(0- ∞), and C_{max} will be evaluated for dose proportionality using a power model (where log-dose acts as an explanatory variable) to estimate ratios of dose-normalized geometric least square (LS) means and corresponding 90% confidence intervals (CIs). The power model will be:

log(parameter) = log(dose) + participant + error.

Example SAS code:

```
proc mixed data = xxx;
by parameter;
model log_pk = log_dose / alpha = 0.1 cl solution outpred=resids ddfm = kr2;
estimate 'xx mg' intercept 1 log_dose yy / alpha = 0.1 cl; /* log value of xx */
estimate 'zz mg - xx mg' log_dose pp / alpha = 0.1 cl; /* pp = diff in log values of zz and xx*/
ods output solution = est estimates = estims;
run;
```

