Eligible participants will be admitted to the clinical research unit (CRU) on Day -1. Participants will receive a single-dose administration on Day 1 and will remain inpatient for approximately 7 days followed by visits at regular intervals.

A total of IV dose cohorts (CC) mg and mg) and SC dose cohorts mg and mg) are planned. Cohort 4 will include Japanese participants and Cohorts 6, 7,

and 8 will include Japanese and Chinese participants. The study intervention will be administered as a single dose on Day 1, followed by a 12-week follow-up period (Section 1.2).

Within each dose cohort, treatment-matched placebo will be given using the same time, frequency, and route as LY3872386, as applicable.

Part B: MAD of LY3872386 in Patients with Atopic Dermatitis

Eligible patients with AD will receive multiple doses of LY3872386 within a 12-week treatment period, with administration at an interval of at most CCI and/or at least CCI. Each dosing and discharge are at the discretion of the investigator, with visits in between the doses and at regular intervals following the last dose of the study drug.

At least 2 IV and/or SC dose cohorts (CC) mg and CC mg) are planned. The study intervention is planned to be administered on Day 1, followed by dose administration and/or CC for up to 12 weeks in patients with AD. The route and frequency of administration are planned to be the same for all participants within a cohort. The dose, route, and frequency of administration will be confirmed based on emerging data from the safety and PK data of previous SAD and MAD cohorts. Participants will be followed up for 14 weeks after the last dose (Section 1.2).

Within each dose cohort, treatment-matched placebo will be given using the same time, frequency, and route as LY3872386, as applicable.

Part C: Open-label Multiple Doses of Prednisone in Healthy Participants

Eligible participants will be admitted to the CRU on Day -2. Participants will receive multiple doses of either CCI may of prednisone during 1 treatment period.

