Table KMAA.1. Summary of Participants in Cohorts Dosed with LY3872386

Part A: SAD of LY3872386 in Healthy Participants ^a								
Cohort #	Planned Dose /	Numbe	Number of		Number of		er of	Total Number
	Administration	Planned Non-		Planned		Planned		of Planned
	Route	Japanese /		Japanese		Chinese		Completers
		Non-Chinese		Participants		Participants		
		Participants						
		LY	PBO	LY	PBO	LY	PBO	
Cohort 1	mg IV							
Cohort 2	mg IV				 .			_
Cohort 3	ccl mg IV	LY: PBO						per cohort
Cohort 5	mg SC							
Cohort 4b	CCI mg IV	GC!						
Cohort 6 ^c	ccl mg IV							
Cohort 7 ^c	ccl mg SC	CCI						per cohort
Cohort 8c	CCI mg IV	_	_	_	_	_	_	_
Part B: MAD of LY3872386 in Patients with AD								
Cohort #	Planned Dose/ Administration Route	of Ra						Total Number of Planned Randomized Patients
Cohort 1	CCI mg IV or SC	LY: PBO					CCI	
Cohort 2	CC mg IV or SC	CC LY: PBO					CCI	

Abbreviations: AD = atopic dermatitis; IV = intravenous; LY = LY3872386; MAD = multiple-ascending dose, PBO = placebo; SAD = single-ascending dose; SC = subcutaneous.

Table KMAA.2. Summary of Participants Dosed with Prednisone

Part C: Multiple Doses of Prednisone in Healthy Participants								
Dosing Group	Planned Dose/Administration Route	Total Number of Planned Completers						
Group 1	mg PO	CCI						
Group 2	mg PO	CCI						
Group 3	mg PO	oci ·						

Abbreviation: PO = oral administration.

a Sentinel dosing will be used.

b Sentinel pair must be non-Japanese and non-Chinese participants OR Sentinel pair must be mixed ethnicities (non-Japanese/non-Chinese participant and Japanese participant).

^c Sentinel pair must be non-Japanese and non-Chinese participants.

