10. STATISTICAL METHODOLOGY

10.1 General

For Part A, TFLs may be presented separately by race and ethnicity (e.g., Overall, Japanese, Chinese, and non-Japanese/non-Chinese), as appropriate.

Data listings will be provided for all data that is databased. Summary statistics and statistical analysis will only be presented for data where detailed in this SAP. For continuous data, summary statistics will include the arithmetic mean, arithmetic standard deviation (SD), median, minimum, maximum, and number of observations; for log-normal data (e.g., the PK parameters: AUCs and C_{max}) the geometric mean and geometric coefficient of variation (CV%) will also be presented. For categorical data, frequency count and percentages will be presented. Data listings will be provided for all participants up to the point of withdrawal, with any participants excluded from the relevant population highlighted. Summary statistics and statistical analyses will generally only be performed for participants included in the relevant analysis population. For the calculation of summary statistics and statistical analysis, unrounded data will be used.

For change from baseline summary statistics, each individual change from baseline will be calculated by subtracting the individual participant's baseline value from the value at that time point. The individual participants' change from baseline values will be used to calculate the summary statistics (arithmetic mean, arithmetic SD, median, minimum, maximum, and number of observations) using a SAS procedure such as Proc Univariate.

Data analysis will be performed using SAS® Version 9.4 or greater.

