10.2 Demographics and Participant Disposition

Participant disposition will be listed. The demographic variables age, sex, race, ethnicity, country of enrolment, site ID, body weight, height and body mass index will be summarized by part and treatment and listed. All other demographic variables will be listed only.

In Part B, baseline disease characteristics CCI will also be summarized by treatment and listed.

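### The Part A dose-proportionality model has no body-weight term, although planned Japanese and Chinese enrolment shifts the make-up of the later IV cohorts, so a body-size effect may be read as a dose effect

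*SAP*

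**What the plan says.** The analysis in SAP 10.3.2 is headed "Dose Proportionality (Part A IV doses only" and applies to log AUC and log Cmax. It is meant "to estimate ratios of dose-normalized geometric least square (LS) means and corresponding 90% confidence intervals (CIs". The formula is "log(parameter) = log(dose) + participant + error", and the code reads "model log_pk = log_dose / alpha = 0.1 cl solution outpred=resids ddfm = kr2". Neither contains a term for weight, ethnicity or cohort. The participant term does not stand in for one: each Part A participant receives a single dose and contributes one value per parameter, so that term cannot be separated from the residual, and the code has no random statement.

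By Table 1 and Section 7 of the SAP, the IV cohorts are 1, 2, 3, 4, 6 and 8, and Cohorts 5 and 7 are SC. Doses are in mg, not mg/kg.

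On who enters which cohort, the Protocol synopsis says "Cohort 4 will include Japanese participants and Cohorts 6, 7" and goes on to name Cohort 8, with Japanese and Chinese participants in the last three. Protocol Table KMAA.1, "Summary of Participants in Cohorts Dosed with LY3872386", splits numbers by ethnic group for Cohorts 4 and 6 to 8, but gives Cohorts 1, 2, 3 and 5 one undivided allocation.

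Two other SAP provisions bear on the point. Section 10.1 says "For Part A, TFLs may be presented separately by race and ethnicity". Section 10.2 says "body weight, height and body mass index will be summarized by part and treatment and listed".

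**The concern.** A power model estimates how exposure changes with dose, and it attributes to dose whatever else changes along the dose axis. Here ethnic mix changes along it by plan. If Japanese and Chinese participants weigh less on average, and exposure per mg is higher in lighter people, the later cohorts have higher dose-normalised exposure for a reason unrelated to dose. The slope then lies above 1 and the 90% CI is centred on the wrong value even when kinetics are proportional.

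The question is a live one for this compound. Protocol 2.2 reports monkey exposure to the conjugate as roughly proportional on Day 1 and more than proportional on Day 85. A body-size effect of the kind described would push the human estimate in that same direction, and the planned fit could not tell the two apart. The sponsor also treats body size as relevant to exposure: Protocol 4.3 scales human kinetics allometrically and computes dose multiples per kg.

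**Working it through.** The plan gives no slope, precision or sample-size figure for this analysis, so there is nothing to reproduce. The check asks how far an omitted weight effect could move the estimate.

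**From the documents:** six IV cohorts, log dose as the only regressor, flat mg doses, planned Japanese/Chinese enrolment in Cohorts 4, 6 and 8, and 90% CIs.

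**Assumed, because redacted or absent:**
- IV doses rise with cohort number and are evenly spaced on the log scale, coded x = 0, 1, 2, 3, 4, 5.
- Active n = 6, 6, 6, 6, 10, 10.
- The Japanese/Chinese share f is 0 in Cohorts 1 to 3, 25% to 50% in Cohort 4, and 40% to 67% in Cohorts 6 and 8.
- The mean weight ratio r (Japanese/Chinese to others) is 0.80 to 0.95.
- Exposure is proportional to weight^(-k), with k = 0.5 to 1.0.

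**Formula.** The log exposure shift per affected participant is d = -k ln(r). With a true slope of 1, the bias per dose step is d × Sxf/Sxx, and the top-to-bottom dose-normalised ratio is inflated by exp(5 d Sxf/Sxx). Under even log spacing this does not depend on the fold range of doses.

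**Common terms.** N = 44; mean x = 126/44 = 2.864; Sxx = 494 - 126²/44 = 133.18.
- Low shares (25%, 40%): Sxf = 40.5 - 126 × 9.5/44 = 13.30, so 5 Sxf/Sxx = 0.499.
- High shares (50%, 67%): Sxf = 69.3 - 126 × 16.4/44 = 22.34, so 5 Sxf/Sxx = 0.839.

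| r | k | d | Ratio, low shares | Ratio, high shares |
|---|---|---|---|---|
| 0.95 | 0.5 | 0.0256 | 1.013 | 1.022 |
| 0.85 | 0.75 | 0.1219 | 1.063 | 1.108 |
| 0.80 | 1.0 | 0.2231 | 1.118 | 1.206 |
| 1.00 | any | 0 | 1.000 | 1.000 |

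**Against the interval width.** The half-width on the log ratio is t(0.95; 42) × 5s/√Sxx = 1.682 × 5s/11.54, with s = √ln(1 + CV²). For CVs of 20%, 30% and 40%, s is 0.198, 0.294 and 0.385, and the half-width is a factor of about 1.16, 1.24 and 1.32. The bias is smaller than this in most combinations; the exceptions are the strongest case at low CV.

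**Coverage by simulation** (true slope 1, residual log SD 0.25, within-group log-weight SD 0.15). Unadjusted 90% CI coverage was about:
- 0.90 for r = 0.95, k = 0.5, low shares;
- 0.86 for r = 0.85, k = 0.75, low shares;
- 0.77 to 0.78 for r = 0.85, k = 0.75, high shares;
- 0.57 to 0.61 for r = 0.80, k = 1, high shares (two separate runs).

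With log weight in the model, coverage was 0.89 to 0.90 and the mean ratio 0.995 to 1.001 throughout. With equal mean weights there was no bias either way, and at k = 0.75 the covariate still reduced the standard error of the log ratio from 0.118 to 0.109, about 8%.

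**The case against.** The strongest reply is that this is a descriptive secondary analysis and the confounding is hypothetical. Protocol 9.3.3.2 makes the power model conditional on the data, no significance test is planned, and no acceptance limit is set. The documents give no weight difference between groups and no relation between weight and exposure. The Part A BMI range of 18 to 32 applies to everyone. The SAP permits separate displays by ethnicity, tabulates weight by treatment, and allows extra model-based analyses, so an imbalance would be visible. An unadjusted power model is also a legitimate summary of exposure against mg dose.

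Much of this stands. It limits the seriousness of the point and argues against replacing the planned fit. It does not repair that fit. SAP 10.3.2 states the analysis without the Protocol's condition, and its ratio and 90% CI are exactly what would be off-centre. Separate displays are optional and leave the overall estimate unchanged. Separate fits would rest on at most three IV dose levels for planned Japanese enrolment and two for Chinese. A common BMI range does not equalise weight when heights differ.

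The simulation is also partly circular: weight was the only assumed route from ethnicity to exposure, so adjusting for weight had to work. If the groups differ by another route, the weight-adjusted slope can still be biased.

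A reader might also infer that Cohorts 1 to 3 contain no Japanese or Chinese participants. The documents do not say so: those cohorts carry no quota, and Protocol 4.1 opens the study to any ethnicity. Cohorts 6 and 8 must also include at least a non-Japanese, non-Chinese sentinel pair. The confounding is therefore partial, and that overlap helps make a weight effect estimable.

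**Conclusion.** The point holds as a possible, design-linked confounding that the SAP leaves unexamined. Under the assumptions above, the top-to-bottom dose-normalised ratio is inflated by about 1% to 21%, and by roughly 6% to 11% in middle cases. Coverage is close to nominal in mild cases and clearly below it in the stronger ones. If mean weights are equal the bias is zero; the upward direction holds only if Japanese and Chinese participants are lighter. That Cohorts 4, 6 and 8 are the higher IV doses is inferred from the ascending design, since the values are redacted.

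Two stronger readings are tempting and not supported. One is that body size will be read as a dose effect: that needs a weight difference and a weight-exposure relation, and the documents establish neither. The other is that this slope drives dosing in Part B. Protocol 4.3 and 6.6.1 rest those decisions on emerging safety, PK and PD data, with safety and tolerability primary for escalation. In Protocol 9.4.1 the data reviews that justify the opening MAD doses follow SAD Cohorts 4 and 5, then 6 and 7, so neither requires Cohort 8. A third review falls at the end of Part A, but does not mention the power model. SAP 11 plans no interim statistical analyses.

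**What to change.** In SAP 10.3.2, add a prespecified second fit with centred log baseline body weight, `model log_pk = log_dose log_wt_c`, with the other options unchanged. Report its slope, dose-normalised ratios and 90% CIs next to those of the unadjusted power model, and state that a material difference between the two will be discussed as possible confounding by body size. A fit restricted to non-Japanese, non-Chinese participants may be added to look for ethnic differences not due to weight, accepting wider intervals.

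The cost is 1 degree of freedom in the added fit and an extra table row. No new data are needed: the Part A schedule records weight at screening and again before dosing.

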9.3.3.2. Pharmacokinetic Statistical Inference

The descriptive statistics for the PK parameters will be provided for each dose level or route of administration. Where appropriate, the geometric mean and geometric coefficient of variation will be reported. If data allows, the dose proportionality for LY3872386 may be assessed for AUC and C_{max} using a power model to estimate the slope of the power model, which represents the ratio of dose-normalized geometric means.

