3. INTRODUCTION

This SAP has been developed after review of the Clinical Study Protocol (final version dated 01 September 2023).

This SAP describes the planned analysis of the safety, tolerability, pharmacokinetic (PK), and pharmacodynamic (PD) data from this study. A detailed description of the planned TFLs to be presented in the clinical study report (CSR) is provided in the accompanying TFL shell document.

The intent of this document is to provide guidance for the statistical and PK analyses of data. In general, the analyses are based on information from the protocol, unless they have been modified by agreement with Eli Lilly and Company. A limited amount of information concerning this study (e.g., objectives, study design) is given to help the reader's interpretation. This SAP must be finalized prior to first participant visit. When the SAP and TFL shells are agreed upon and finalized, they will serve as the template for this study's CSR.

This SAP supersedes the statistical considerations identified in the protocol; where considerations are substantially different, they will be so identified. If additional analyses are required to supplement the planned analyses described in this SAP, they may be performed and will be identified in the CSR. Any substantial deviations from this SAP will be agreed upon with Eli Lilly and Company and identified in the CSR. Any minor deviations from the TFLs may not be documented in the CSR.

This SAP is written with consideration of the recommendations outlined in the International Conference on Harmonization (ICH) E9 Guideline entitled Guidance for Industry: Statistical Principles for Clinical Trials¹ and the ICH E3 Guideline entitled Guidance for Industry: Structure and Content of Clinical Study Reports².

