10.3 Pharmacokinetic Assessment

10.3.1 Pharmacokinetic Analysis

The following PK parameters will be determined using noncompartmental methods in validated software program Phoenix WinNonlin (Certara, Version 8.3.5 or higher):

Plasma concentrations of LY3872386, total antibody, LY3558533 (free payload) will be used to determine the following PK parameters for Parts A and part B, where possible:

CONFIDENTIAL Protocol Reference: J4L-MC-KMAA

For Part A - SAD (Cohorts 1 to 8):

Parameter	Units ^a	Definition
AUC(CCI)	μg.h/mL	area under the concentration versus time curve from time 0 to hours post dose.
AUC(CCI)	μg.h/mL	area under the concentration versus time curve from time 0 to hours post dose.
AUC _(0-t)	μg.h/mL	area under the concentration versus time curve from time 0 to the time of the last quantifiable concentration.
$\mathrm{AUC}_{(0-\infty)}$	μg.h/mL	area under the concentration versus time curve from time 0 to infinity
$\%AUC_{(tlast-\infty)}$	%	fraction of AUC(0-∞) extrapolated
C_{max}	$\mu g/mL$	maximum observed drug concentration
t_{max}	h	time of the maximum observed drug concentration
t _{1/2}	h	half-life associated with the terminal rate constant (λ_z) in non-compartmental analysis
CL/F	L/h	apparent total body clearance of drug calculated after extra-vascular administration (for LY3872386 only)
V _z /F	L	apparent total body clearance of drug calculated after extra-vascular administration (for LY3872386 only)
CL	L/h	total body clearance of drug calculated after intravenous administration (for LY3872386 only)
Vz	L	Volume of distribution during terminal phase (LY3872386 IV dosing)
F	%	bioavailability of drug. Fraction of extravascular dose reaching the general circulation compared to an IV administration

^a Units are based on concentration units (provided by the bioanalytical lab or preferred units for presentation of PK parameters) and dose units used in the study.

For Part B - MAD (Cohorts 1 and 2), Profile Day 1 and Day 85:

Parameter	Unitsa	Definition
AUC _(0-t)	μg.h/mL	area under the concentration versus time curve from time 0 to the time of the last quantifiable concentration. b
AUC_{τ}	μg.h/mL	area under the concentration versus time curve during one dosing interval
$\mathrm{AUC}_{(0-\infty)}$	μg.h/mL	area under the concentration versus time curve from time 0 to infinity ^b
$\%AUC_{(tlast-\infty)}$	%	fraction of AUC(0- ∞) extrapolated
C_{max}	$\mu g/mL$	maximum observed drug concentration

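### SAP 10.3.2 promises dose-normalised ratios, but its model and example contrast estimate the raw ratio of geometric means, and no normalising step is stated

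*SAP*

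**What the plan says.** SAP 10.3.2 applies a power model to log AUC(0–tlast), AUC(0–∞) and Cmax for the Part A IV doses. Its stated purpose is "to estimate ratios of dose-normalized geometric least square (LS) means and corresponding 90% confidence intervals (CIs"). The model is given as "log(parameter) = log(dose) + participant + error".

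The example code has "model log_pk = log_dose / alpha = 0.1 cl solution outpred=resids ddfm = kr2". It then forms a between-dose contrast, "estimate 'zz mg - xx mg' log_dose pp / alpha = 0.1 cl", and a code comment defines pp as the difference between the log values of zz and xx. The code ends by saving the log-scale estimates to datasets.

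Protocol 9.3.3.2 describes the same analysis more loosely and as optional. There the model is used "to estimate the slope of the power model, which represents the ratio of dose-normalized geometric means".

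SAP 12 reports no changes from the protocol's analyses.

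**The concern.** The result that the SAP names and the result that its model and contrast produce are different quantities. The named result should equal 1 when exposure rises in proportion to dose. The contrast as coded equals the dose multiple in that case.

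No sentence or code line in either document divides the parameter by dose, subtracts the log dose ratio or uses b − 1. A programmer who follows the text and code literally, and adds only the exponentiation that any log-scale analysis needs, would put the raw ratio under a dose-normalised label. AUC and Cmax are the secondary PK endpoints, so this mislabelled figure could reach the clinical study report.

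**Working it through.** **Inputs.** All come from SAP 10.3.2: the response is `log_pk`, the regressor is `log_dose`, and the contrast coefficient is pp = ln(zz) − ln(xx) = ln(r), with r = zz/xx. The CI level is 90% (alpha = 0.1). The documents give no numerical result for this analysis and the doses are redacted, so there is no figure to reproduce. The values of r, the slopes and the slope CIs below are assumptions.

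**What the code estimates.** The fitted line is log(PK) = a + b·ln(dose). The contrast is

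(a + b·ln zz) − (a + b·ln xx) = b·ln(r),

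and exp(b·ln r) = r^b = GM(zz)/GM(xx), the raw ratio of geometric means.

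**What the text names.** The dose-normalised ratio is

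[GM(zz)/zz] ÷ [GM(xx)/xx] = r^b ÷ r = r^(b−1) = exp(b·pp − pp).

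The quotient of the two is r, whatever the slope. Since pp is a known constant, the same factor applies to both CI limits and the log-scale standard error does not change.

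**Size for assumed values.** Each entry is r^b or r^(b−1), evaluated at the slope and at its CI limits.

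| r | Slope b (90% CI) | Coded contrast, exponentiated | Dose-normalised ratio |
|---|---|---|---|
| 2 | 1.0 (0.90–1.10) | 2.00 (1.87–2.14) | 1.00 (0.933–1.07) |
| 10 | 1.0 (0.90–1.10) | 10.0 (7.94–12.6) | 1.00 (0.794–1.26) |
| 100 | 1.0 (0.90–1.10) | 100 (63.1–158) | 1.00 (0.631–1.58) |
| 2 | 0.8 (0.70–0.90) | 1.74 (1.62–1.87) | 0.871 (0.812–0.933) |
| 10 | 0.8 (0.70–0.90) | 6.31 (5.01–7.94) | 0.631 (0.501–0.794) |

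**Simulation check.** Each Part A participant receives one dose, so the participant term in the equation cannot be separated from error. The code omits it, and the fit is ordinary regression. There were 5,000 runs with assumed doses of 1, 3, 10, 30, 60 and 100, six participants per dose, a log-scale SD of 0.3 and a true b of 1. For the 100-fold comparison:

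- The coded contrast averaged 100.1 (geometric mean). Its 90% CI covered the raw ratio of 100 in 90.5% of runs and covered 1 in 0%.
- After subtracting pp, the average was 1.001 and the CI covered 1 in 90.5% of runs.
- In one simulated dataset, refitting with log(parameter/dose) as the response changed the slope from 0.955 to −0.045, that is b − 1, with the same standard error (0.0337).

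**The protocol wording.** If the slope itself were read as the ratio, b = 0.8 would be reported as 0.80 for every dose range. The dose-normalised ratio is 0.871 over a 2-fold range and 0.631 over a 10-fold range. The two agree for every range only when b = 1.

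**Cross-check elsewhere in the plan.** SAP 10.3.1 lists 13 Part A parameters. None is AUC/dose or Cmax/dose by name, but clearance after IV dosing of LY3872386 is dose/AUC(0–∞). Its ratio between doses is r ÷ r^b = r^(1−b), the reciprocal of the dose-normalised AUC(0–∞) ratio.

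**The case against.** The code is headed as an example and stops on the log scale, so it reports no ratio of any kind. A further step is needed in any case, and removing pp there is trivial. The table shells might show it: the SAP says a detailed description of the outputs "is provided in the accompanying TFL shell document", which was not available for this review. This stands, and it limits the claim to what the two documents state. It does not remove the gap, because the written model equation lacks the normalisation as well and the SAP text is where the estimate should be defined.

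The slope already answers the scientific question. This also stands: b and its 90% CI are correct and the model statement requests them. A supposed dose-normalised ratio equal to the dose multiple would also look odd beside a slope near 1. IV clearance gives a second check, but only for LY3872386 AUC(0–∞), not for Cmax or AUC to the last quantifiable time.

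The analysis carries little inferential weight. Protocol 9.3.3.2 makes it optional, and there are no formal hypotheses. That is fair, although SAP 10.3.2 commits to the analysis without that condition.

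The protocol wording need not compete with the SAP. SAP 3 says the SAP supersedes the protocol's statistical section, so correcting the SAP is enough.

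**Conclusion.** The point holds as a mismatch between a named estimate and the method given for it. Exponentiating the contrast as written yields r^b where the text calls for r^(b−1). The discrepancy is exactly the dose ratio, for the estimate and both CI limits. That factor follows from the algebra and rests on no assumption. Only the worked values do, because the real doses are redacted.

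A reader might infer three stronger things that the documents do not support:

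- That the study report will contain wrong ratios. This cannot be known, because the back-transformation step and the table shells are not in the documents.
- That the power model or the assessment of proportionality is invalid. It is not: the slope and its CI are unaffected, and no formal test depends on the contrast.
- That nothing in the PK plan is adjusted for dose. IV clearance in effect is.

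The harm is limited to a mislabelled secondary PK estimate, and it arises only if pp is not removed before reporting. It is worth correcting because the remedy costs almost nothing.

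**What to change.** In SAP 10.3.2, state that pp is subtracted from the contrast estimate and from both 90% CI limits before exponentiating, and add that step to the example code. Using log(parameter/dose) as the response is equivalent. Report the resulting ratio, (zz/xx)^(b−1), beside b and its 90% CI, and confirm that the table shells carry the same definition.

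Optionally, correct the sentence in Protocol 9.3.3.2 that equates the slope with the dose-normalised ratio. Protocol 9.3.1 requires an amendment only for a change to a principal feature, so this can wait for the next amendment or be noted in the clinical study report.

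The cost is one SAP sentence and one code step, plus one optional protocol sentence. No new data are needed. SAP 3 says "This SAP must be finalized prior to first participant visit", so the definition can be settled without reference to results.
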